#### 3.2 Primary and secondary outcomes

#### **Primary outcome**

Uptake and feasibility of recruitment and research procedures

Uptake will be assessed both quantitatively and qualitatively. The quantitative assessment will include the range and average number of sessions attended by participants, as reported by cultural facilitators, while the qualitative assessment will explore reasons for non-attendance and barriers to engagement among participants. To enhance practicality, attendance will be measured based on sessions attended with the link worker, alongside standardized measures of the types of cultural activities recommended and attended, and self-reported participation in these activities. Feasibility of recruitment procedures will be evaluated by measuring the time required to recruit 100 participants, the number of individuals screened, and the number of eligible individuals who chose not to participate, as reported by GPs. Feasibility of research procedures will be assessed through the proportion of participants who complete follow-up assessments at each timepoint and the extent of missing data at both baseline and follow-ups. These measures will provide insights into the practicality of implementing the intervention and conducting research within this population. A measure of uptake will also be applied to the control group to evaluate if they did independently engage in cultural activities.

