#### 3.4. Study intervention

A **link worker from the Città di Lugano** will contact participants to provide detailed information about the available cultural offerings and the research procedure. The link worker will work closely with participants to understand their personal preferences and interests, ensuring that the selected cultural activities align with their tastes and needs. By tailoring the experience to each participant, the link worker will help identify the most appropriate events or activities that can enhance their engagement and overall well-being, while also supporting the goals of the research study.

Participants will receive up to six sessions with their link worker, which is a pragmatic allocation based on trial feasibility, though in real-world practice, individuals may receive additional support if needed. Each session will last up to one hour and will be conducted in person, over the phone, or via video call, depending on participant preference and accessibility.

All cultural activities will be **fully funded**, ensuring that financial barriers do not limit participation. The available activities are part of a curated set designed specifically for this program, including drawing, painting, music, photography, museotherapy, dance, and theater. Link workers will not have complete autonomy over referrals but will guide participants toward these pre-selected activities that align with the research framework. Each type of activity will include up to 25 weekly sessions, lasting 1-2 hours each and taking place at LAC. All activities will be facilitated by a cultural facilitator.

We propose participatory artistic activities, as opposed to more passive cultural experiences (such as being a spectator at events). This choice is grounded in the belief that active participation in the creative process fosters deeper emotional engagement, enhances personal expression, and can have therapeutic benefits for mental and physical well-being. By engaging participants in hands-on artistic creation, we aim to encourage a sense of accomplishment and connection to the cultural experience, as well as promote social interaction and personal growth.

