#### 4.2 Recruitment, screening and informed consent procedure

The recruitment process will follow a number of steps (see Figure 1). Patients will be screened by their general practitioners (GPs) during routine appointments to confirm eligibility. Access to a GP is a prerequisite for inclusion in the study. To facilitate this process, the research team will provide GPs with a **structured screening form** (see the document "Formulario reclutamento") to assess whether patients meet the inclusion criteria. Along with the screening form, GPs will receive a **standardized gridline** (see the document "Griglia introduzione studio") to help introduce the study to the patient in a consistent and clear manner. If a patient is deemed eligible and expresses interest in participating, the GP will forward their contact details to the **research team at the Institute of Family Medicine** using the structured screening form.

Once referred, potential participants will be contacted over the phone to **confirm interest and schedule the baseline assessment**. Within three days from this phone call, potential participants will receive a written confirmation of their appointment (date, time, and address) and an **information sheet at home**, including a study description and a copy of the consent form (see document *ICF*), allowing them to review the materials before their baseline assessment.

GPs will **not** be responsible for handling consent forms but will collect and document key recruitment data, including the total number of individuals screened and those invited to participate, through a structured form provided by the research team (see the document "Rapporto screening"). This information will help estimate eligibility rates, assess recruitment efficiency, and inform planning for a larger-scale randomized controlled trial (RCT).

Figure 1. Recruitment process

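### Attendance in the primary outcome rests on two different session counts with no stated order, and a refusal count taken from GPs alone can miss people who decline after referral

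*Protocol*

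**What the plan says.** Attendance and uptake belong to the primary objective (section 3.1) and to the primary outcome (section 3.2). The quantitative part of uptake in section 3.2 starts with "the range and average number of sessions attended by participants, as reported by cultural facilitators". Section 3.4 has the cultural facilitators running the activities, so this is a count of classes.

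The same paragraph, giving practicality as the reason, then says that "attendance will be measured based on sessions attended with the link worker". It sets this count beside two other measures: a standardised record of which kinds of activity each person was advised to join and did join, and what participants themselves report about taking part.

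Section 3.4 shows how far apart the two kinds of session are. For the link worker: "Participants will receive up to six sessions with their link worker", held face to face, by telephone or by video. For the courses: "Each type of activity will include up to 25 weekly sessions, lasting 1-2 hours each and taking place at LAC".

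On recruitment, section 3.2 will use "the number of eligible individuals who chose not to participate, as reported by GPs". Section 4.2 describes the GP report as "including the total number of individuals screened and those invited to participate". It then has the research team telephone each referred person and take consent at the baseline visit. GPs do not handle the consent forms.

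**The concern.** The link-worker meeting is the step at which a person is matched to an activity. The classes are the activity prescribed, and section 3.4 presents active participation in them as the reason for the programme. The two counts answer different questions: whether people engage with referral, and whether they take part in what they were referred to. With two bases and no order between them, the attendance result can be chosen after the data are seen. On the link-worker basis alone, someone who goes to no class still registers attendance.

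The refusal count raises a related problem of source. GPs forward only eligible patients who express interest. Someone who changes their mind at the phone call or at consent does so with the research team, so a count defined by what GPs report can miss them. Section 4.2 says the recruitment data will help plan a larger randomised trial. An undercount would make recruitment for that trial look easier than it is.

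**Working it through.** The protocol gives no attendance target and no refusal figure, so there is nothing to reproduce. The check sets the definitions side by side and works simple ratios.

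**Attendance: inputs**
- Link-worker sessions: at most 6 (section 3.4).
- Course sessions: at most 25 (sections 3.4 and 4.3).
- Experimental group: 80 (section 3.3).

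**Attendance: extreme case**, all link-worker meetings and no classes:
- link-worker count: 6/6 = 100%
- facilitator count: 0/25 = 0%
- both pooled: 6/(6 + 25) = 6/31 = 19.4%

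Six is a ceiling and not a target, so 100% is not a score that the protocol itself assigns. The case shows only that the two counts are not interchangeable.

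**Does another section settle it?**
- Synopsis, Statistical Considerations: session attendance, type of session not stated.
- Section 5.1: range and average of sessions attended, type not stated.
- Section 3.4: attendance at the prescribed events will be monitored. The class data will therefore exist, but this does not make them the primary measure.

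No section ranks or combines the counts.

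**Denominator.** Section 3.1 speaks of attendance rates, whereas sections 3.2 and 5.1 report numbers of sessions. Section 5.2 replaces people who withdraw before starting the activity and does not say whether they stay in the attendance result. If *k* people are replaced and the 80 who remain attend a mean proportion *p* of sessions, the mean over everyone assigned is 80*p*/(80 + *k*), which is below *p* whenever *k* > 0.

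**Refusals.** Let *G* be eligible people who decline at the GP, *L* those who decline at the phone call or consent visit, and 100 the number who consent (the planned sample, ignoring replacements). Eligible people number 100 + *G* + *L*. The GP-only refusal rate is *G*/(100 + *G* + *L*). The full rate is (*G* + *L*)/(100 + *G* + *L*). The protocol gives neither *G* nor *L*. Purely for illustration, assume *G* = 30 and let *L* run from 0 to 30:

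| *L* (assumed) | Eligible | GP-only rate | Full rate |
|---|---|---|---|
| 0 | 130 | 30/130 = 23.1% | 30/130 = 23.1% |
| 15 | 145 | 30/145 = 20.7% | 45/145 = 31.0% |
| 30 | 160 | 30/160 = 18.8% | 60/160 = 37.5% |

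The gap is *L*/(100 + *G* + *L*): zero if nobody declines after referral, and larger as more do. The table shows the direction of the error and is no evidence of its size.

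**The case against.** A reader might infer that link-worker meetings replace course sessions, so that good attendance could be reported from empty classrooms. The protocol does not support that. The facilitator count stays in the same paragraph, and the link-worker count is set beside the activities attended and self-reported participation. Section 3.4 monitors attendance at the events, and section 5.1 summarises reasons for not completing the intervention. No threshold or category of attender is defined. A person with no classes would show as zero on the facilitator count. Attendance is also only one component of the primary outcome, together with recruitment time, numbers screened and declining, follow-up completion and missing data. In a descriptive pilot, no test or progression rule turns on the choice of count. All of this stands, and it limits the point to an unranked pair of definitions.

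It can also be said that a proportion in place of a mean is a detail for the analysis plan, and that section 4.3 gives one common schedule, so the courses need not differ in length. This is fair as far as it goes: nothing shows that they will differ. But the two bases are set by the protocol's own outcome definition, which is the place to settle them.

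On refusals, the list of GP data in section 4.2 is worded as inclusive and the form itself is not shown, so it may hold more. The research team receives the referrals and takes consent, so referrals minus consents would recover part of the loss after referral. That also stands. The subtraction does not separate people who declined from those not reached or found ineligible, nor does it show the step or the reason. Section 3.2 as written still names GPs as the only source.

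**Conclusion.** The concern holds in a limited form. Section 3.2 gives attendance two non-equivalent bases, course sessions (up to 25) and link-worker sessions (up to 6), without naming one as primary, and neither the synopsis nor section 5.1 resolves it. In the extreme case they differ as 0/25 from 6/6. How often participants would fall near that extreme is unknown.

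The refusal count, taken from GPs alone, can understate refusals because two points of decline come after referral. This rests on reading sections 3.2 and 4.2 together and on GPs not being told of later decisions, which the protocol neither states nor excludes. The size is unknown, and every refusal count used above is assumed.

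Both matters deserve correction before recruitment, because these descriptive figures are the main product of a feasibility study. The class data are collected in any case, so the attendance ambiguity loses no information. The step and reason of a refusal after referral may not be recoverable if nobody records them at the time.

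**What to change.** In section 3.2, name one primary attendance measure: for each person assigned to the experimental group, facilitator-recorded course sessions attended divided by sessions offered in that person's course. Score 0 for anyone who never starts, including those replaced under section 5.2 and those who withdraw before being matched to a course. Report link-worker sessions and self-reported participation as separate measures. Use the same wording in the synopsis (Statistical Considerations) and in section 5.1, so that both say which sessions are meant.

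For recruitment, count those who decline at each step: at the GP, at the research team's phone call, at the consent visit and after assignment. Keep the GP report for the first step and add a short research-team log, with reasons where given, for the others.

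The cost is a few sentences and a simple log. Facilitators already report attendance, and the research team already makes the calls and takes consent. The one real price is that the attendance figure may look less favourable, because people who never start count as zero.

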## The GP will assess the appropriateness of participation based on the individual's clinical profile.

We also envisioned a number of **exclusion criteria** to ensure the appropriateness of participant selection and the feasibility of the intervention. We will exclude:

- Individuals who are still in employment (as the study focuses on retirees). Those who
  undertake occasional freelance work or small consultancies (e.g., fewer than 8 hours per
  week) may still be eligible, provided their professional activities do not interfere with
  participation in the study.
- Individuals with diagnosed moderate to severe dementia or cognitive impairment that affects their ability to provide informed consent
- Individuals with significant mobility restrictions that would prevent engagement in artistic and cultural activities (unless safe accommodations can be arranged)

These criteria ensure that the study includes individuals who can actively participate in cultural prescribing interventions while considering medical appropriateness and potential barriers to engagement.

[figure not shown]

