The research team at the Institute of Family Medicine at the Ospedale Italiano in Lugano will manage the collection of consent forms during the baseline assessment, ensuring that participants fully understand the study before signing and before any study-related procedures. Participants will be asked if they have any questions before signing the document. The investigators will explain to each participant the nature of the study, its purpose, the procedures involved, the expected duration, the potential risks and benefits and any discomfort it may entail. Each participant will be informed that the participation in the study is voluntary and that he or she may withdraw from the study at any time and that withdrawal of consent will not affect his or her subsequent medical assistance and treatment.

The participant will be informed that his or her medical records may be examined by authorised individuals other than their treating physician. All participants for the study will be provided a participant information sheet and a consent form describing the study and providing sufficient information for participant to make an informed decision about their participation in the study (at least one week). The formal consent of a participant, using the approved consent form, will be obtained before the participant is submitted to any study procedure. The consent form will be signed and dated by the investigator or his designee at the same time as the participant sign. A copy of the signed informed consent will be given to the study participant. The consent form will be retained as part of the study records.

The first study participant will be included in the trial within two months following the issuance of the authorization by the Ethics Committee. The investigator or the sponsor notifies the Ethics Committee of the first study participant, in accordance with art 62 lit. c ClinO, resp. art 38 ClinO.

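### Refusals are counted only from GP reports, although referred patients can still decline at steps the GP does not run, so the count is too low whenever anyone declines after referral

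*Protocol*

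**What the plan says.** The primary outcome in section 3.2 assesses recruitment through three quantities. Two are given as "measuring the time required to recruit 100 participants, the number of individuals screened"; the third is "the number of eligible individuals who chose not to participate, as reported by GPs". Only the third measures refusal, and its source is fixed as the GP.

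Section 4.2 sets out the recruitment path:

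- **GP step.** "If a patient is deemed eligible and expresses interest in participating, the GP will forward their contact details to the" research team.
- **Call.** "Once referred, potential participants will be contacted over the phone to" "confirm interest and schedule the baseline assessment". The research team makes this call.
- **Post.** The appointment letter, information sheet and a copy of the consent form reach the patient at home within three days of the call. The patient is to have at least a week to decide.
- **Consent visit.** "The research team at the Institute of Family Medicine at the Ospedale Italiano in Lugano will manage the collection of consent forms" at baseline. The section states that consent forms are not the GP's task.

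The GP's own reporting form is described as including "the total number of individuals screened and those invited to participate". Section 4.2 says this information is meant to support planning of a larger RCT. Section 5.1 returns to the time needed to reach 100, follow-up completion and missing data, but adds no refusal count from the research team.

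**The concern.** The data source named for refusals covers only the first of several points at which a patient can say no. Everyone who is referred has already said yes to the GP. A person who then changes their mind is still an eligible individual who chose not to take part, yet the GP neither runs nor observes the later steps, and the protocol describes no report back to the GP.

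What is at stake is a component of the primary outcome of a feasibility study. How many patients decline once they have the full written information, and why, is something the pilot should hand to the RCT. If these refusals are not logged as they occur, no later analysis plan can recover the reasons.

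**Working it through.** The protocol states no refusal or acceptance rate, so there is no figure to reproduce. The check has two parts.

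**1. Who observes each step (section 4.2 against the source named in section 3.2)**

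| Step | Run by | Refusal visible to GP? | Refusal log in the protocol? |
|---|---|---|---|
| Screening and first interest | GP | Yes | Yes, GP report |
| Telephone call | Research team | No | None described |
| Reading the posted sheet | Patient at home | No | None described |
| Attending the baseline visit | Research team | No | None described |
| Signing consent | Research team | No | None described |

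Section 4.3 has reasons for dropout recorded, but in the context of attrition from study assessments. That does not reach people who never consented.

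**2. Direction and possible size**

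GP-reported refusals = all refusals − refusals after referral. The direction follows at once: any refusal after referral makes the count too low.

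For size, let g be acceptance at the GP, p at the call and c at consent. Only the figure of 100 enrolled comes from the protocol. The values of g (50-70%), p and c (80-100% each) are assumptions, and every loss after referral is treated as a refusal.

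- Referred = 100 / (p × c)
- Invited = referred / g
- Refusals seen by the GP = invited − referred
- Later refusals = referred − 100
- Acceptance from GP data = referred / invited = g
- Acceptance over all steps = 100 / invited = g × p × c

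Worked case, g = 0.70 and p = c = 0.90: referred = 100 / 0.81 = 123; invited = 123.5 / 0.70 = 176; GP-seen refusals = 176 − 123 = 53; later refusals = 123 − 100 = 23. The share of refusals missed is 23.5 / (52.9 + 23.5) = 31%. Acceptance over all steps is 0.70 × 0.81 = 57%, against 70% from GP data.

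| g | p | c | Invited | GP-seen refusals | Later refusals | Share missed | GP-based acceptance | All-step acceptance |
|---|---|---|---|---|---|---|---|---|
| 0.50 | 1.00 | 1.00 | 200 | 100 | 0 | 0% | 50% | 50% |
| 0.50 | 0.90 | 0.90 | 247 | 123 | 23 | 16% | 50% | 41% |
| 0.50 | 0.80 | 0.80 | 312 | 156 | 56 | 26% | 50% | 32% |
| 0.70 | 1.00 | 1.00 | 143 | 43 | 0 | 0% | 70% | 70% |
| 0.70 | 0.90 | 0.90 | 176 | 53 | 23 | 31% | 70% | 57% |
| 0.70 | 0.80 | 0.80 | 223 | 67 | 56 | 46% | 70% | 45% |

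The largest gap is 70.0% − 44.8% = 25 percentage points. If acceptance were instead computed as enrolled / (enrolled + GP-reported refusals), the worked case gives 100 / (100 + 53) = 65%. The gap is smaller, 65% against 57%, but in the same direction.

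**The case against.** The strongest reply is that little is really lost. The protocol defines no participation rate, so there is no stated formula to be wrong. The time taken to enrol 100 lengthens with every late loss and is not biased by this gap. GPs report how many they invited, each referral reaches the research team on a form, and signed consents are kept, so consented over invited could be computed from records already planned.

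Much of this stands. It limits the point to the refusal count and to any rate built on it. But the subtraction is not planned in the protocol. It would also mix refusal with failed contact and with ineligibility found at baseline, where Appendix 1 places the check of inclusion and exclusion criteria, and it gives no reasons. Nor is this a detail that an analysis plan can supply afterwards, because it concerns what is recorded during recruitment.

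A reader might be tempted to go further in three ways that the document does not support:

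- **That recruitment feasibility as a whole is biased.** Refusal is one of three recruitment measures.
- **That most refusals must come late, because the burden of visits, blood draws and the watch first appears in the posted sheet.** GPs introduce the study from a standard guide (*Griglia introduzione studio*) whose content is not shown and which may cover these.
- **That patients set aside under the rule "The GP will assess the appropriateness of participation" go uncounted.** The GP form (*Rapporto screening*) is not shown, its description is not exhaustive, and the rule stands in the eligibility section, so such patients can be read as not eligible.

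**Conclusion.** The point holds for the refusal count. Section 3.2 names a source that cannot see refusals after referral, section 4.2 describes several such opportunities, and nothing in the protocol records them. The count is too low whenever any of them is used, and an acceptance rate derived from it for the RCT would be too high.

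Only the direction is established by the protocol. Under the assumed ranges, 0% to 46% of refusals would be missed and acceptance overstated by 0 to 25 percentage points. Both are zero if nobody declines after referral. This is a gap in data capture that should be closed before recruitment starts; it does not invalidate the other recruitment measures.

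**What to change.** In section 3.2, and carried into section 5.1, change the source of the refusal count to: *as reported by GPs up to referral and by the research team thereafter*.

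From the start of recruitment, have the research team log every referred person who does not enrol, in one of these categories and with a brief reason:

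- declined at the call
- could not be reached
- did not attend baseline
- found ineligible at baseline
- declined consent

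Report refusals at every stage, and report consented divided by eligible as the participation figure.

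The cost is a short log kept by staff who already make the calls and take consent. The reported participation figure may look less favourable than one based on GP reports alone.
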